10.2. Objectives and Statistical Hypotheses

10.2.1. Primary Objectives and Statistical Hypotheses

Objectives: To compare efficacy endpoints of CBR and PFS evaluated by the BIRC based on RECIST v1.1 in one experimental arm (SHR-1210 in combination with apatinib).

Null Hypothesis: SHR-1210 in combination with apatinib PFS at 6 month of 37%.

Alternative Hypothesis: SHR-1210 in combination with apatinib PFS at 6 month of 60% or higher.

10.2.2. Key Secondary Objectives and Statistical Hypotheses

Objective: To compare the OS (assessed by BIRC according to RECIST) of SHR-1210 in combination with apatinib.

Hypothesis: The OS (assessed by BIRC according to irRECIST) of SHR-1210 combined with Apatinib Mesylate tablets (experimental arm) is superior to Apatinib (previous study).

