10.1. Sample Size Determination

According to our previous phase II trial of single agent of apatinib on advanced osteosarcoma, the 4-m PFS rate was 56.76% (95% CI 39.43%–70.84%) and the 6-m PFS rate was 36.77% (95% CI 21.48%–52.16%). 9/37 (24.32%) patients was progression free at 6 months. Median PFS and OS were 4.44 (95% CI 3.12–7.08) and 8.77 (95% CI 6.73–16.70) months, respectively. This trial was designed to discard a PFS at 6 month of 37% (null hypothesis) aiming to reach a PFS at 6 month of 60% or higher (alternative hypothesis). Using Simon’s optimum two-stage design and setting α -error at 0.05 and β -error at 0.10, the presence of at least six successes in the 12 patients enrolled in the first stage allowed the trial to proceed to the second stage in which 31 more patients were needed to be enrolled for the minimum total of 43 patients. Power and sample calculations were performed using EAST® 6.4.1. software package.

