10.3. Analysis Populations

- **Full Analysis Set (FAS):** In line with the Intention-to-Treat (ITT) principle, this population will include all randomized subjects who receive at least 1 dose of study treatment. Subjects will be included in the experimental arm to which they are randomized.
- **Safety Analysis Set (SS):** This population will include all treated subjects who receive at least 1 dose of study treatment. For most subjects, this will be the experimental arm to which they are randomized. For subjects who take incorrect study treatment for the entire treatment period, safety data will be analyzed based on the treatment they actually receive.
- **Anti-drug Antibody (ADA) Analysis Set:** This population will include all subjects who receive SHR-1210 in combination with apatinib and had at least 1 ADA measurement.

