10.4.5. Primary Efficacy Endpoints Analyses

The two primary endpoints for the study are CBR and PFS (assessed by BIRC base on RECIST v1.1). Using Simon's optimum two-stage design and setting α -error at 0.05 and β -error at 0.10, the presence of at least six successes in the 12 patients enrolled in the first stage allowed the trial to proceed to the second stage in which 31 more patients were needed to be enrolled for the minimum total of 43 patients.

The hypothesis testing of OS and PFS will be evaluated by comparing SHR-1210 plus apatinib in FAS using a stratified Log-rank test (based on randomization stratification factors). The PFS and OS curves for experimental arm will be estimated using the Kaplan-Meier (KM) product-limit method. A 95% CI for median OS will be estimated by Brookmeyer-Crowley method. The analysis of OS will be repeated without the stratification factors included in the analysis. Wilcoxon test will also be performed, as well as other methods, if needed.

Detail of multiplicity control can be found in Section 10.4.10.

Further detail, including censoring rules, will be provided in the SAP.

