10.4.10. Multiplicity

PFS hypothesis will be tested at $\alpha=0.005$ (one-sided) and OS hypothesis will be tested at $\alpha=0.02$ (one-sided). If either hypothesis is significant at its initial one-sided α level, its α will be re-allocated to the other endpoint to be tested at $\alpha=0.025$ one-sided. A nominal alpha of 0.01% will be spent on testing the OS hypothesis at the time of the planned PFS analysis. For the interim analysis (70% events) and final analysis of OS endpoint, the Lan-DeMets O'Brien-Fleming spending function was used to control the type I error.

When both the PFS analysis and OS (interim or final) analysis tests are significant, ORR assessed by BIRC according to RECIST v1.1 may be tested at 0.025 one-sided (alpha re-allocation).

Any changes to the above strategy will be documented elsewhere, if not in a protocol amendment, at the earliest time before any formal analysis is being conducted.

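### The OS superiority test against the previous apatinib study has no comparator data, and a one-sample test against that study's median would not hold the stated alpha

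*Protocol*

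**What the plan says.** Section 3.1 describes a single-arm trial of about 43 subjects. Section 10.2.2 sets the OS hypothesis against an external comparator: the combination ("experimental arm) is superior to Apatinib (previous study").

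Section 10.4.10 attaches confirmatory machinery to it:
- The level is set by "OS hypothesis will be tested at $\alpha=0.02$ (one-sided"), and it rises to 0.025 if PFS is significant.
- There is an early look: "A nominal alpha of 0.01% will be spent on testing the OS hypothesis at the time of the planned PFS analysis".
- There is an interim at 70% of OS events with O'Brien-Fleming-type spending.
- ORR may be tested only when PFS and OS are both significant. Section 10.4.6 repeats this gate and there calls OS a primary endpoint.

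For the method, section 10.4.5 states: "The hypothesis testing of OS and PFS will be evaluated by comparing SHR-1210 plus apatinib in FAS using a stratified Log-rank test". The strata are said to be randomization factors, and no second group is named. Section 10.3 defines the FAS so that "this population will include all randomized subjects who receive at least 1 dose of study treatment". Neither the FAS nor any other set in 10.3 includes patients from the earlier study.

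The only OS result given for that study is in section 10.1: a median of 8.77 months (95% CI 6.73–16.70), in a study of 37 patients. No OS event number, target effect or power is given.

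**The concern.** The hypothesis is about true survival on the combination against true survival on apatinib. A test of it needs information on both, with the uncertainty of both. The plan supplies patients for one side only, so the 0.02 belongs to no analysis that can be carried out.

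A team that notices this will probably replace the two-group log-rank test with a one-sample test against 8.77 months. That test can be run on the FAS, but it answers a different question: whether the median exceeds 8.77 months, rather than whether it exceeds the true median on apatinib. The earlier estimate is about as uncertain as the new one will be. If it happened to fall low (its interval reaches 16.70 months), a combination that adds nothing to survival could be reported as superior much more often than 2% of the time.

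The result also matters beyond OS, because 10.4.10 uses it to re-allocate alpha to PFS and to open the ORR test.

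**Working it through.** **The plan's own figure.** The one-sided split adds up: 0.005 (PFS) + 0.02 (OS) = 0.025. There is no OS event number or power to reproduce.

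**Uncertainty of the earlier median (section 10.1).** On the log scale, SE = [ln(16.70) − ln(6.73)] / (2 × 1.96) = 0.232. Under exponential survival SE = 1/√D, so this corresponds to D = 1/0.232² ≈ 18.6 effective deaths. The upper limit is 37, if every earlier patient had died.

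**Deaths in this trial (assumed).** The follow-up statements differ. Section 4.6 puts the last visit about 18 months after the last enrolment. Section 16 has the last enrolment in January 2019 and study end in June 2019, about 5 months later. With 43 patients enrolled over 12 months and an exponential median of 8.77 months, simulation gives about 36 and 24 deaths respectively. The grid below runs from 15 to 43.

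**True size if 8.77 months is treated as known.** The test divides the log difference by the new trial's SE alone. When true OS is equal, the variance of that difference is 1/D_new + 1/D_hist. Hence

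size = 1 − Φ( z / √(1 + D_new/D_hist) ), with z = 2.054 at 0.02 and 1.960 at 0.025.

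Example: D_new = 36 and D_hist = 18.6 give √(1 + 36/18.6) = 1.713, then 2.054/1.713 = 1.199, so the size is 11.5%.

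Size at nominal 0.02:

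| D_hist | D_new 15 | 24 | 36 | 43 |
|---|---|---|---|---|
| 18.6 | 6.3% | 8.7% | 11.5% | 13.0% |
| 25 | 5.2% | 7.1% | 9.4% | 10.7% |
| 37 | 4.2% | 5.5% | 7.2% | 8.1% |

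At nominal 0.025 the same grid runs from 4.9% (D_hist 37, D_new 15) to 14.1% (D_hist 18.6, D_new 43).

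**Simulation check.** 40,000 trials were simulated per scenario, with equal exponential OS, 37 earlier and 43 new patients, and nominal 0.02. The earlier study's follow-up was varied over three windows (6–18, 12–24 and 30–40 months).

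| Analysis | About 24 new deaths | About 36 new deaths |
|---|---|---|
| One-sample log-rank, earlier estimate treated as known | 5.5–7.0% | 7.5–9.5% |
| One-sample log-rank, true survival known | 1.4% | 1.3–1.5% |
| Two-sample, earlier study's variance included | 1.9–2.1% | 2.0–2.2% |

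The excess comes from ignoring the earlier study's sampling error, and it disappears when that error is carried.

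**The case against.** A reader might infer that the protocol fixes the old result as a constant and that its OS test therefore has a false-positive rate of 6–12%. The documents do not support that. No section says that 8.77 months is the OS null; it appears only as background to the sample size. The named methods (stratified log-rank and Wilcoxon tests in 10.4.5, hazard ratios in 10.4.11) are two-group methods. The FAS wording refers to randomized subjects in a trial that randomizes nobody, so it is weak evidence of how the earlier patients would enter. The earlier study is the investigators' own, so a patient-level comparison is conceivable, and it would hold about 2%.

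Fixed historical benchmarks are also ordinary in single-arm phase II trials. Section 10.1 turns an estimated 36.77% into a 37% null in the same way. If the OS null were simply a median of 8.77 months, there would be no inflation.

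Finally, the size figure is soft. The printed interval is asymmetric on the log scale: the lower half implies SE 0.135 and the upper half 0.329. With those values, the formula gives about 3–5% or 10–17% at nominal 0.02 for 15–35 deaths.

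These points stand as limits on the size and on what may be attributed to the text. They do not rescue the plan. The null in 10.2.2 names apatinib, not a number. The hypothesis, alpha, gate and analysis sets are all fixed in the protocol, so this is not detail left to an SAP, and together they do not define a test. The harm passed on to ORR cannot be quantified, because the ORR test in 10.4.6 also compares treatment groups that do not exist.

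**Conclusion.** The concern holds in this form: the OS superiority comparison is undefined and cannot be run as written, so the one-sided 0.02 (or 0.025) is not the error rate of any analysis described. Substituting a one-sample test against the earlier median would leave the stated hypothesis tested at roughly 4–13% instead of 2%, or 5–14% instead of 2.5%.

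Those ranges are conditional on that substitution, which the protocol does not state. They assume 15–43 new deaths, about 19–37 effective historical deaths, and log-normal error with one average SE. Using either half of the printed interval alone would widen them. They cover sampling error only: differences in patients or period between the two studies, and the interim look, are not modelled. The change should be made, although OS does not drive the sample size.

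**What to change.** - **10.2.2 and 10.4.5:** make OS descriptive. Report Kaplan-Meier OS with a 95% CI, shown beside the earlier 8.77 months (95% CI 6.73–16.70), with no superiority claim.
- **10.4.10:** delete the OS alpha, the 0.01% look, the 70% interim and OS as a gate for ORR. Make 10.4.6 consistent.
- **If a comparison is kept:** define it in 10.3 and 10.4.5 as a supportive, non-randomised two-sample analysis using the earlier study's patient-level data. Report a hazard ratio with a CI that carries that study's sampling error, and make no confirmatory claim.

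This is a wording amendment and needs no new patients. The optional comparison needs access to the earlier study's OS data. The cost is the formal OS superiority claim, which the design cannot support at the stated level.

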10.3. Analysis Populations

- **Full Analysis Set (FAS):** In line with the Intention-to-Treat (ITT) principle, this population will include all randomized subjects who receive at least 1 dose of study treatment. Subjects will be included in the experimental arm to which they are randomized.
- **Safety Analysis Set (SS):** This population will include all treated subjects who receive at least 1 dose of study treatment. For most subjects, this will be the experimental arm to which they are randomized. For subjects who take incorrect study treatment for the entire treatment period, safety data will be analyzed based on the treatment they actually receive.
- **Anti-drug Antibody (ADA) Analysis Set:** This population will include all subjects who receive SHR-1210 in combination with apatinib and had at least 1 ADA measurement.

10.4. Statistical Analysis Methods

10.4.1. General Method

This is a parallel group, controlled study. All statistical tests, unless otherwise specified, will be analyzed by experimental arms and using the appropriate statistics according to the data type. Summary statistics for continuous variables will include the mean, standard deviation, median, and range (minimum/maximum). Categorical variables will be presented as frequency counts and percentages. Time-to-event variables will be summarized by Kaplan Meier (K-M) medians and 95% confidence intervals.

10.4.2. Subject Disposition

The number of subjects enrolled, treated, discontinued and those with major protocol

deviations will be counted. The primary reason for study drug and/or study discontinuation will be summarized according to the categories in the eCRF. The end of study status (alive, dead, withdrew consent or lost to follow-up) at the data cutoff date will be summarized.

10.4.3. Demographics and Baseline Characteristics

Demographic and other baseline characteristics will be summarized using descriptive statistics. Continuous variables include age, weight, vital signs, time since initial cancer diagnosis, and time since advanced/metastatic disease diagnosis; categorical variables include, gender, ECOG-PS score, geographical region, country, race, metastatic site, and macrovascular invasion and/or extrahepatic spread status etc.

10.4.4. Prior and Concomitant Medications

Concomitant medications will be coded using the WHO Drug Dictionary drug codes. Prior and concomitant medications will be summarized and listed by drug and drug class. Prior medications will be defined as medications taken within 28 days of the first dose of study drug that were stopped prior to study drug administration. Concomitant medications will be defined as medications that 1) started before the first dose of study drug and were continuing at the time of the first dose of study drug, or 2) started after the first dose of study drug. Prior and concomitant medications will be listed.

10.4.5. Primary Efficacy Endpoints Analyses

The two primary endpoints for the study are CBR and PFS (assessed by BIRC base on RECIST v1.1). Using Simon's optimum two-stage design and setting α -error at 0.05 and β -error at 0.10, the presence of at least six successes in the 12 patients enrolled in the first stage allowed the trial to proceed to the second stage in which 31 more patients were needed to be enrolled for the minimum total of 43 patients.

The hypothesis testing of OS and PFS will be evaluated by comparing SHR-1210 plus apatinib in FAS using a stratified Log-rank test (based on randomization stratification factors). The PFS and OS curves for experimental arm will be estimated using the Kaplan-Meier (KM) product-limit method. A 95% CI for median OS will be estimated by Brookmeyer-Crowley method. The analysis of OS will be repeated without the stratification factors included in the analysis. Wilcoxon test will also be performed, as well as other methods, if needed.

Detail of multiplicity control can be found in Section 10.4.10.

Further detail, including censoring rules, will be provided in the SAP.

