| Study Design | 
This is a Single-arm, Open label, Prospective, Single-center Clinical Trial to evaluate the efficacy and safety of PD-1 antibody SHR-1210 plus Apatinib Mesylate Tablets in patients with advanced Osteosarcoma.
 
Primary efficacy endpoint is 6 months PFR based on RECIST v1.1, and approximately 38 subjects who could be evaluated will be enrolled.
 
Subjects will receive study treatment after being informed of all pertinent aspects of the study, signing the informed consent form and passing the screening for eligibility. SHR-1210, 200 mg, via intravenous infusion, once every two weeks (Q2W) + Apatinib Mesylate Tablets 500 mg, p.o., once per day (QD), continuously, 4 weeks (28 days) per cycle of therapy, until meeting the criteria for study treatment termination specified in the protocol. Subjects will continue to receive safety and survival follow-up after end of treatment. Subjects who discontinue treatment for reasons other than progression of disease will continue to receive regular radiological evaluation follow-up after end of treatment.
 
Subjects will have safety visits on D1 of every 2 cycles; Radiological examination will be performed once every 8 weeks to evaluate efficacy until progression of disease is determined (non-pseudoprogression), start of a new anti-tumor therapy, withdrawal of informed consent, death, or termination of the study by the sponsor, whichever comes first.
 |
| Study Drug | 
SHR-1210 for Injection (Generic Name: Camrelizumab for Injection) (Manufacturer: Suzhou Suncadia Biopharmaceuticals Co., Ltd.)
 
Apatinib Mesylate Tablets (Manufacturer: Jiangsu Hengrui Medicine Co., Ltd.)
 |
| Route of Administration | 
SHR-1210 200 mg will be infused intravenously (premedication is not required). Each infusion will be administered over 30 min (no less than 20 min, no more than 60 min), once every two weeks;
 
Apatinib Mesylate Tablets 500 mg is administered orally after meals within 30 min, once per day, continuously.
 |
| Inclusion Criteria | 
Subjects can be enrolled in this study only when they meet all the inclusion criteria:
 
 1. Provided informed consent and sign the informed consent form; 2. ≥ 11 years old, male and female; |

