| 
Data Analysis / Statistical Methods
 | 
Efficacy Analyses
 
The two primary endpoints for the study are PFR (base on RECIST v1.1).
 
PFR will be evaluated by stratified Log-rank test and the corresponding 95% confidence interval (CI) will be estimated in a stratified Cox proportional hazard model. The PFS and OS curves will be estimated using the Kaplan-Meier (KM) product-limit method. A 95% CI for median PFS and OS will be estimated by Brookmeyer-Crowley method.
 
ORR and DCR will be assessed according to RECIST v1.1. ORR and DCR according to RECIST v1.1 will be performed using stratified Cochran-Mantel-Haenszel (CMH) test at 0.025 one-sided. Difference in proportions for ORR and DCR, and their 95% CI using normal approximation will be provided.
 |

| | |
|---------------------|---|
| | 
Overall response rates and their corresponding 95% exact CIs will be calculated by Clopper-Pearson method.
 
The other time-to-event endpoints will be estimated using the Kaplan-Meier (KM) product-limit method, unless specified. A 95% CI for median survival time will be estimated by Brookmeyer-Crowley method, if necessary.
 
For other binary variables, stratified CMH test will be used and two-sided 95% CI for treatment difference will be calculated using normal approximation.
 
Safety Analyses
 
Safety data including Adverse events (AEs) and laboratory results will be summarized descriptively using summary statistics.
 
Other Analyses:
 
Exploratory endpoints including average scores and its change from baseline obtained from EORTC QLQ-C30 will be summarized descriptively using summary statistics.
 |
| End of Study | 
For this study, end of study is defined as the date of the Last Patient's Last Visit (LPLV).
 |
| Study Period | 
Estimated enrollment for first subject in: Jan 2018
 
Estimated enrollment for last subject in: Jan 2019
 
Estimated end of study: Jun 2019
 |

SCHEDULE OF ACTIVITIES

| Item/evaluation time | Screening period ^a | Treatment period | | Follow-up period | |
|---|-------------------------------|------------------|------------------------|-------------------------------------|------------------------|
| | | Treatment period | End-of treatment visit | Every 8 weeks in 36 weeks until PDb | End-of treatment visit |
| | | D1 | D15 | D8 | D29 |
| Signature of informed consent form | X | | | | |
| Determination of inclusion / exclusion criteria | X | | | | |

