3. STUDY DESIGN

3.1. Overall Design

This is a Single-arm, Open label, Prospective, Single-center phase II trial to evaluate the efficacy and safety of PD-1 antibody SHR-1210 plus apatinib mesylate as seconde/third-line therapy in patients with advanced osteosarcoma.

The study will be conducted in subjects with incurable, locally advanced or metastatic osteosarcoma who had progressed upon first-line/second-line chemotherapy including high-dose methotrexate, doxorubicin, cisplatin with or without ifosfamide. Primary efficacy endpoints include both CBR and PFS evaluated by the BIRC based on RECIST v1.1, and approximately 43 subjects will be enrolled. Eligible subjects will receive SHR-1210 combined with apatinib mesylate (experimental arm).

Subjects will receive study treatment after being informed of all pertinent aspects of the study, signing the informed consent form and passing the screening for eligibility. Experimental arm: SHR-1210, 200 mg, via intravenous infusion, once every two weeks (Q2W) + apatinib mesylate 500 mg, p.o., once per day (QD), continuously, 4 weeks (28 days) per cycle of therapy, until meeting the criteria for study treatment termination specified in the protocol. Subjects will continue to receive safety and survival follow-up after end of treatment. Subjects who discontinue treatment for reasons other than progression of disease will continue to receive regular radiological evaluation follow-up after end of treatment.

The subject will continue to receive study treatment until intolerable toxicity occurs, or until lack of clinical benefits as determined by investigator after comprehensive evaluation of radiological and laboratory examination data as well as the subject's

clinical condition (e.g., tumor symptomatic exacerbation), or until the subject voluntarily withdraws from study treatment, whichever comes first.

Following disease progression in accordance with RECIST v1.1 (evaluated by investigator), subjects may continue treatment with SHR-1210 monotherapy or in combination with apatinib, if they can still clinically benefit from and tolerate study treatment as determined by investigator (see Section 6.6 for treatment criteria after disease progression).

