10. STATISTICAL ANALYSIS

A statistical analysis plan (SAP) will be prepared to provide further details regarding the definition of analysis variables and analysis methodology to address all study objectives. The SAP will serve as a compliment to the protocol and where there is a discrepancy between the SAP and protocol, the SAP will supersede it. Any critical revision within the SAP of definition(s) or analysis method(s) for the primary endpoints will be included in a protocol amendment.

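### The efficacy tests are written for a randomised controlled trial and cannot be run in this single-arm study; the two-stage test that does fit has conflicting alpha levels and cannot reach the stated power of 0.90

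*Protocol*

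**What the plan says.** **Design.** Section 3.1 states: "This is a Single-arm, Open label, Prospective, Single-center phase II trial". The title and the synopsis agree.

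**Primary hypothesis.** Sections 10.1 and 10.2.1 set a 6-month PFS rate of 37% (null) against 60% or higher. The design is a Simon optimum two-stage design with alpha 0.05 and beta 0.10. The stage 1 rule is that "the presence of at least six successes in the 12 patients enrolled in the first stage allowed the trial to proceed" to stage 2, which adds 31 patients for a minimum total of 43. No final rejection cut-off is given. The synopsis (Study Design) says instead that "approximately 38 subjects who could be evaluated will be enrolled".

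**Primary analysis.** Section 10.4.5 repeats the Simon parameters. Its next paragraph sets out how the PFS and OS hypotheses are tested, in these words: "evaluated by comparing SHR-1210 plus apatinib in FAS using a stratified Log-rank test (based on randomization stratification factors"). In the synopsis the corresponding sentence is "PFR will be evaluated by stratified Log-rank test", with a confidence interval from a stratified Cox model.

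**Other analyses.**
- The synopsis and 10.4.6 specify stratified CMH tests and treatment differences for ORR and other binary endpoints.
- 10.4.7 uses a stratified Cox model for time to deterioration.
- 10.4.11 plots hazard ratios by subgroup.
- 10.4.1 calls the study parallel-group and controlled.
- The FAS in 10.3 is defined so that the "population will include all randomized subjects who receive at least 1 dose of study treatment".

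**Comparator.** Only 10.2.2 names one: OS on the combination "is superior to Apatinib (previous study").

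**Multiplicity.** Section 10.4.5 refers to 10.4.10. That section tests PFS at one-sided 0.005 and OS at one-sided 0.02, with re-allocation up to 0.025 and an interim OS analysis. Section 10.5 repeats the interim analysis.

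**The concern.** A log-rank test, a treatment hazard ratio and a CMH test each compare at least two groups. The FAS of this trial contains one. There was no randomisation, so there are no randomisation strata to adjust for. The sentence that sets out hypothesis testing for the primary endpoint therefore describes something that cannot be done.

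A reader who falls back on the Simon design meets two further problems. The alpha for the primary claim differs by a factor of up to ten between sections, and the printed stage 1 rule does not look compatible with a power of 0.90.

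The protocol thus does not settle which test, at which level and with which cut-off, decides success. In an open-label trial that choice could be made with results in view. Readers are also given a power that the design does not have.

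**Working it through.** **Inputs.** p0 = 0.37 and p1 = 0.60 (10.2.1). Stage 1 has n1 = 12, continuing with at least 6 successes; stage 2 has 31, so N = 43; stated alpha 0.05 and beta 0.10 (10.1). PFS alpha is 0.005, or 0.025 after re-allocation (10.4.10). The synopsis gives 38 evaluable subjects. Section 10.1 does not state sidedness; the Simon test is one-sided by construction.

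**1. Can the stated power be reproduced?** A trial must pass stage 1 before it can succeed, so power cannot exceed P(X1 ≥ 6), with X1 ~ Binomial(12, p).

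At p = 0.60, the probabilities of 0 to 5 successes are 0.0000, 0.0003, 0.0025, 0.0125, 0.0420 and 0.1009, which sum to 0.1582.

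P(X1 ≥ 6) = 1 − 0.1582 = 0.8418.

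No stage 2 size and no final cut-off can give 0.90. The stage 1 pass probability reaches 0.90 only if the true rate is about 0.638. At p = 0.37 it is 0.2588.

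**2. Operating characteristics with N = 43.** For a final cut-off c:

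P(reject | p) = Σ over x = 6 to 12 of P(X1 = x) · P(X2 ≥ c − x), with X2 ~ Binomial(31, p).

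| Reject if at least | alpha (p = 0.37) | power (p = 0.60) |
|---|---|---|
| 20/43 | 0.0779 | 0.832 |
| 21/43 | 0.0499 | 0.819 |
| 22/43 | 0.0292 | 0.795 |
| 23/43 | 0.0156 | 0.754 |
| 24/43 | 0.0076 | 0.693 |
| 25/43 | 0.0034 | 0.610 |

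The lowest admissible cut-off is 21 at alpha 0.05 (10.1), 23 at 0.025 and 25 at 0.005 (10.4.10). A result of 21 or 22 successes is positive only under 10.1. A result of 23 or 24 is positive under 10.1 and at 0.025, but not at 0.005.

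**3. Which design do the printed numbers match?** I searched exhaustively for the Simon optimum at 37% against 60%, alpha 0.05.

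- Beta 0.10: n1 = 20, continue with at least 9, N = 44, reject with at least 22 (alpha 0.0462, power 0.901).
- Beta 0.20: n1 = 12, continue with at least 6, N = 38, reject with at least 19 (alpha 0.0489, power 0.805).

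The printed stage 1 rule is that of the beta 0.20 design, and its N of 38 matches the evaluable number in the synopsis. If 10% dropout is assumed (the protocol states no rate), 38/0.90 = 42.2, which rounds up to 43. That this is where the numbers came from is an inference. The ceiling of 0.842 is not.

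**4. Sensitivity to the attained N.** The protocol calls 43 a minimum, and the cut-off moves with N. With the same stage 1 rule:

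- at least 21/42: alpha 0.0404, power 0.808
- at least 22/44: alpha 0.0369, power 0.809 (keeping 21 would give alpha 0.0603)
- at least 22/45: alpha 0.0455, power 0.820

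**5. Unknown 6-month status (assumption).** Suppose 5% or 10% of would-be successes cannot be assessed and count as failures. The effective rate is 0.60 × 0.95 = 0.57 or 0.60 × 0.90 = 0.54, and power at 21/43 falls to 0.736 or 0.631.

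**The case against.** The strongest reply is that 10.4.5 opens with the Simon design and 10.2.1 gives matching hypotheses, so a workable test stands in the same section and the log-rank text is template carry-over. It is fair that the intended test is probably the Simon test. But the section presents Simon as the design and continuation rule, and the sentence that deals with hypothesis testing names the log-rank test. No final cut-off is printed, and the section then refers to 10.4.10, whose alpha differs.

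A second reply is that 10.4.5 also provides for OS without stratification and for a Wilcoxon test, and 10.2.2 names the previous apatinib study, so an unstratified historical OS comparison could be run. It could, but the analysis is stated within the FAS, which holds one group, and nothing says how the earlier study's data would enter. It would in any case not rescue the primary endpoint.

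A third is that the SAP supersedes the protocol. The SAP may supply omitted detail such as censoring rules. Here the protocol fixes tests that do not apply, and section 10 itself says that a critical revision of "analysis method(s) for the primary endpoints will be included in a protocol amendment".

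Three limits stand. The protocol does not show when the primary test was or will be settled, so choice after seeing results is a risk and not an established fact. The missing-status powers in step 5 rest on a rule the protocol does not state. The subgroup and time-to-deterioration wording would be editorial on its own.

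**Conclusion.** The point holds and must be fixed. The log-rank, Cox, CMH and hazard-ratio analyses cannot be run as written. Kaplan-Meier curves, Brookmeyer-Crowley intervals for medians and Clopper-Pearson intervals for rates can, and should stay.

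The alpha for the primary claim is contradictory (0.05 against 0.005 or 0.025), and outcomes of 21 to 24 successes turn on which section is followed.

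The stated power of 0.90 is unattainable at a 60% rate: the ceiling is 0.842, and with N = 43 and alpha 0.05 it is 0.819. These figures are exact binomial results and assume that 6-month status is known for every patient and that the lowest cut-off holding alpha is used.

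**What to change.** Amend the protocol as follows.

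1. **Synopsis and 10.4.5.** Replace the log-rank, Cox and Wilcoxon text with one primary test: the exact two-stage binomial test of the 6-month rate by BIRC under RECIST v1.1, null 37%, one-sided alpha 0.05, continuing with at least 6 of 12. State the boundary for 43 patients (reject with at least 21) and that it is recalculated by the same exact method if the attained N differs. Record whether it was fixed before stage 2 data were reviewed. Alpha 0.05 is taken because the sample size rests on it; if the sponsor prefers another level, the boundary and power must change with it.
2. **CBR.** Sections 1.1.2 and 1.2.2.2 equate it with the 6-month progression-free rate. If that is meant, say so; otherwise it carries no test, because 10.2.1 gives no hypothesis for it.
3. **10.1.** Restate power as about 0.82 with complete 6-month status, and reconcile 43 with the 38 evaluable. Say how unknown status counts. If it counts as failure, say that power is lower and that the 37% null is the estimated rate (36.77%), not the raw 9/37 (24.32%).
4. **10.4.10 and 10.5.** Delete the 0.005/0.02 split, the re-allocation and the OS interim analysis.
5. **Synopsis, 10.4.6, 10.4.7 and 10.4.11.** Report rates with exact intervals instead of CMH tests and differences, time to deterioration by Kaplan-Meier, and subgroup 6-month rates with exact intervals instead of hazard ratios.
6. **10.2.2.** Report OS descriptively, or label the comparison as non-randomised and historical and give its method.
7. **10.4.1 and 10.3.** Remove the controlled-trial description and define the FAS as enrolled subjects who receive at least one dose. In the same pass, align the time origin: 7.1 counts PFS and OS from randomisation, whereas the synopsis counts the 6-month rate from enrolment.

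The cost is one amendment, with no new patients, visits or data and less analysis than now. The price is disclosing power of about 0.82. Restoring 0.90 would be a redesign and is not proposed here.
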